6.1. Primary Endpoint(s)

6.1.1. Primary Analysis

For each cohort, children will be assigned to 2 groups: Participant in whom a 13vPnC vaccine type (VT) strain has been isolated from the respiratory tract, and participant from whom a 13vPnC VT strain has not been isolated from the respiratory tract (VT carrier versus without VT carrier). Therefore, a total of 4 subgroups are available: 13vPnC cohort with VT carrier; 13vPnC cohort without VT carrier; unvaccinated cohort with VT carrier; unvaccinated cohort without VT carrier.

For each of the 13 serotypes contained in 13vPnC, the IgG concentration and MOPA titers will be transformed in logarithm scale. Crude (unadjusted) geometric mean concentrations (GMCs) and geometric mean titers (GMTs) and 95% confidence interval (CI) will be calculated for the 4 cohort/carriage subgroups.

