8. DATA ANALYSIS/STATISTICAL METHODS

Detailed methodology for summary and statistical analyses of the data collected in this study will be documented in a Statistical Analysis Plan (SAP) and will be maintained by the sponsor.

The number and proportion of subjects with *S. pneumoniae* isolates detected will be summarized for both cohorts: the 13vPnC cohort and unvaccinated cohort. Additionally, the number and proportion of each serotype, serotype included in 13vPnC (VT), and serotypes not included in 13vPnC (non-VT) will be summarized for both cohorts.

For each cohort, children will be assigned to 2 groups: Participant in whom a 13vPnC vaccine type (VT) strain has been isolated from the respiratory tract, and participant from whom a 13vPnC VT strain has not been isolated from the respiratory tract (VT carrier versus without VT carrier). Therefore, a total of 4 subgroups are available: 13vPnC cohort with VT carrier; 13vPnC cohort without VT carrier; unvaccinated cohort with VT carrier; unvaccinated cohort without VT carrier.

For each of the 13 serotypes contained in 13vPnC, the IgG concentration and MOPA titers will be transformed in logarithm scale. Crude geometric mean concentrations (GMCs) and geometric mean titers (GMTs) and 95% confidence interval (CI) will be calculated for the 4 cohort/carriage subgroups.

A multiple regression model will be used with the log concentration or log titers as a dependent variable. Independent variables will include cohort (13vPnC or unvaccinated), 13vPnC VT carriage status, and the interaction of the cohort and carriage status, as well as the confounding variables (age at enrollment, residence location, season of enrollment). Adjusted GMCs (or GMTs) and adjusted geometric mean ratios (GMRs) along with 95% CI will be estimated based on this model. The (GMRs) will compare antibody levels between any 2 of the 4 subgroups, as well as between the 2 cohorts, and between the carriage status.

Additionally, serotype-specific GMC/GMT (or adjusted GMC/GMT) and 95% CI may be provided for each 13vPnC serotype carriage status (Yes/No), for both 13vPnC cohort and unvaccinated cohort. Similar to any 13vPnC VT carriage status, the descriptive comparisons will be presented as GMR (or adjusted GMR) and 95% CI.

All of the analyses are considered as descriptive and no multiplicity adjustment will be made.

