4. ANALYSIS SETS (POPULATIONS FOR ANALYSIS)

Population	Description
Enrolled	All participants who signed the informed consent document.
Evaluable	All participants who signed the informed consent document, met all inclusion/exclusion criteria, and had at least one immunogenicity assay value available for analysis.

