5.2. General Methods

5.2.1. Analyses for Binary Endpoints

For carriage results, the exact 2-sided 95% confidence intervals (CIs) (Clopper-Pearson CIs) will be provided for the proportions of subjects with VT or serotype-specific carriage.

The exact CIs (Clopper-Pearson) for the various proportions of individual groups will be computed using the F distribution. If r is the number of responses and n is the number of subjects, then it follows that $p=r/n$ is the estimate of the proportion of responses. An exact 95% CI can be computed by solving the following 2 equations. For the lower limit P_L ,

$$p_L = \frac{rF_L}{(rF_L + (n - r + 1))}$$

and for the upper limit P_U ,

$$p_U = \frac{(r+1)F_U}{(n-r)+(r+1)F_U}$$

where F_L is the quantile from the F distribution for $\alpha=0.025$, with numerator degrees of freedom equal to $2r$ and denominator degrees of freedom equal to $2(n-r+1)$. F_U is the quantile from the F distribution for $\alpha=0.975$, with numerator degrees of freedom equal to $2(r+1)$ and denominator degrees of freedom equal to $2(n-r)$. When r equals 0, F_L should be set equal to 1.0 so P_L equals 0. When r equals n , F_U should be set equal to 1.0 so P_U equals 1.0.

The CI using the F distribution is described in Collett (1991)¹ and implemented in SAS PROC FREQ.

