5.2.2. Analyses for Continuous Endpoints

For each of the 13 serotypes contained in 13vPnC Cohort and also Non-13vPnC Cohort, GMCs of IgG and GMT of MOPA will be calculated along with 2-sided 95% CIs, which will be constructed by back transformation of the CIs for the mean of the logarithmically transformed IgG/MOPA computed using Student's t distribution. In addition, the 2-sided 95% CI on the geometric mean ratios (GMRs) (the GMC of 13vPnC Cohort to the GMC of Non-13vPnC Cohort and the GMT of 13vPnC Cohort to the GMT of Non-13vPnC Cohort) for all 13 serotypes will be also provided and those 95% CIs will be constructed by back transformation of the CIs for the mean difference of the measures on the logarithmically transformed scale(IgG/MOPA) using Student's t distribution.

A multiple regression model will be used with the log concentration or log titers as a dependent variable. Independent variables will include cohort (13vPnC or unvaccinated), 13vPnC VT carriage status, and the interaction of the cohort and carriage status, as well as the confounding variables (age at enrollment, sex, season of enrollment). Adjusted GMCs (or GMTs) and adjusted geometric mean ratios (GMRs) along with 95% CI will be estimated based on this model. The (GMRs) will compare antibody levels between:

1. Within 13vPnC Cohort: VT-carrier + vs VT-carrier -
2. Within Non-13vPnC Cohort: VT-carrier + vs VT-carrier -
3. 13vPnC Cohort vs Non-13vPnC Cohort
4. Within VT-carrier +: 13vPnC Cohort vs Non-13vPnC Cohort
5. Within VT-carrier -: 13vPnC Cohort vs Non-13vPnC Cohort

Additionally, serotype-specific GMC/GMT (unadjusted) and associated 95% CI will be provided for each 13vPnC VT carriage status (Yes/No), for both 13vPnC cohort and unvaccinated cohort. GMRs (unadjusted) (GMC/GMT of VT- carrier + vs GMC/GMT of VT-carrier -) within 13vPnC Cohort and within unvaccinated Cohort, and GMRs (unadjusted) (GMC/GMT of 13vPnC Cohort vs GMC/GMT of Non-13vPnC Cohort) within

VT-carrier + group and within VT-carrier group and associated 95% CIs will be calculated using Student's t distribution for the mean difference of the measures on the logarithmically transformed scale (IgG/MOPA).

If model adjusted GMCs, GMTs, GMRs are not estimatable (e.g., due to limited data), then only unadjusted GMCs, GMTs, GMRs and associated 95% CIs will be presented.

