5.3. Methods to Manage Missing Data

In general, nonmissing values will not be excluded from the analysis. However, certain statistical procedures that compare 2 or more variables, or values at more than 1 time point, for the same subject require all values to be available. In such cases, nonmissing values will be dropped to the extent necessary to perform the procedure.

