5.3.1. Immunogenicity Data

Immunogenicity data collected for this study are the results of immunologic assays performed by the National Institutes for Food and Drug Control (NIFDC) on the blood samples collected.

The Lower Limit of Quantitation (LLOQ) in micrograms per mL ($\mu\text{g/mL}$) for each serotype is shown in Table 2.

Table 2. The LLOQ in Micrograms per mL from NIFDC

Serotype	LLOQ
1	0.02
3	0.03
4	0.02
5	0.03
6A	0.03
6B	0.03
7F	0.04
9V	0.02
14	0.04
18C	0.02
19A	0.02
19F	0.03
23F	0.03

Antibody concentrations above LLOQ are considered accurate and their quantitated values will be reported. The Limit of detection (LOD) was established as 50% of the LLOQ. Values below the LLOQ or denoted Below Limit of Quantification (BLQ) will be set to **0.5 \times LOD** for analysis.

The NIFDC's OPA LLOQ in titers for all serotypes was set as 8. For the results of antibody titers that are below the LLOQ, or denoted as BLQ, $0.5 \times \text{LLOQ}$ will be assigned for analysis.

No other missing assay data will be imputed in the analyses. All immunogenicity analyses will be performed after the imputation of the antibody concentrations or antibody titers that are below the LLOQ.

For each serotype's antibody concentrations or antibody titers, the number of subjects with missing values at each blood sampling point will be provided.

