6.2.2. Deep Upper Respiratory Aspirates Culture Summaries

The number and proportion of subjects with *S. pneumoniae* isolates detected will be summarized for both cohorts: the 13vPnC cohort and unvaccinated cohort. Additionally, the number and proportion of each serotype, serotype included in 13vPnC (VT), and serotypes not included in 13vPnC (non-VT) will be summarized for both cohorts.

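### Does the two-way carriage definition wrongly count a child with no usable culture as a non-carrier of vaccine-type pneumococcus?

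*SAP*

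**What the plan says.** SAP 6.1.1 puts each child of a cohort in one of two groups: a VT strain was isolated, or the child is a "participant from whom a 13vPnC VT strain has not been isolated from the respiratory tract". With two cohorts this makes four subgroups and no category for unknown status. Protocol 8 says the same.

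The evaluable set (SAP 4) asks for consent, eligibility and that the child "had at least one immunogenicity assay value available for analysis". It does not ask for a culture or serotype result. SAP 6 applies all summaries to that set. For carriage proportions, SAP 5.2.1 describes the denominator only in general terms: "If r is the number of responses and n is the number of subjects".

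Carriage also enters the regression in SAP 5.2.2: "Independent variables will include cohort (13vPnC or unvaccinated), 13vPnC VT carriage status, and the interaction of the cohort and carriage status". The general missing-data rule in SAP 5.3 is that, where a procedure needs several values from one child, "nonmissing values will be dropped to the extent necessary to perform the procedure". For serum results, SAP 5.3.1 promises that "the number of subjects with missing values at each blood sampling point will be provided". There is no equivalent sentence for culture or serotype.

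**The concern.** The negative group is defined by the absence of a finding, not by a valid negative culture. A child whose aspirate was never taken, or whose culture failed, meets that definition word for word. Protocol 6 accepts that some tests will not be feasible, and serotypes come from another study (WI232403) through an ID link, so an isolate may also lack a type.

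Carriage is one of the two factors behind the primary objective. If unknown children are counted as non-carriers, VT carriage is understated whenever one of them is a carrier, and carrier versus non-carrier GMRs are blurred. If carriage is instead set to missing, these children leave the regression. They then also leave the adjusted comparison of the two cohorts, because carriage is in that model. So two readings give different numbers of children, and no planned table counts the children without a usable culture.

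**Working it through.** **Which children are affected**

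- *No usable culture.* Nothing was isolated, so the wording of SAP 6.1.1 does place the child with the non-carriers.
- *Isolate untyped or not linked.* The definition turns on whether a VT strain was isolated, not on whether it was typed. If the isolate is VT, a VT strain was isolated. The text leaves this child's status undetermined; it does not make the child negative. SAP 6.2.2 reports children with any pneumococcus, with VT and with non-VT serotypes, so a shortfall in typing can be roughly inferred.

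**How many there should be**

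Protocol 5.2 and 6.2.2 require an aspirate as a study procedure if none was taken in routine care. Protocol 3 says that all pneumococcal isolates from children hospitalized at the site are typed and their IDs recorded for import. Protocol 3.2 sets the enrolment deadline so that serotype data are ready for the final report, and SAP 7 places that report after all data are available. No expected number is given, so the rates below are assumptions.

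**Effect of the literal reading**

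Inputs: about 300 children, 100 vaccinated and 200 unvaccinated (Protocol 3.3). Assumed: true VT carriage p = 10-30%; share with no usable culture u = 2-10%, unrelated to carriage; true GMR = 2. The number affected is 300 × 0.02 = 6 to 300 × 0.10 = 30.

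- Observed carriage = p(1 − u)
- Share of carriers within the non-carrier group: c = pu / (1 − p(1 − u))
- Observed GMR = 2^(1 − c)

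| p | u | carriage reads | c | GMR reads |
|---|---|---|---|---|
| 10% | 2% | 9.8% | 0.0022 | 1.997 |
| 10% | 10% | 9.0% | 0.0110 | 1.985 |
| 30% | 2% | 29.4% | 0.0085 | 1.988 |
| 30% | 10% | 27.0% | 0.0411 | 1.944 |

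Even at u = 20% and p = 30%, c = 0.06/0.76 = 0.0789 and the GMR reads 1.893.

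If unknown children also differ in antibody by k on the log2 scale, the non-carrier mean shifts by m = [u(1 − p)k + up(1 + k)] / [(1 − u)(1 − p) + u], and GMR = 2^(1 − m). For u = 5-10% and p = 10-30%, two-fold lower antibody (k = −1) gives 2.07-2.14; two-fold higher (k = +1) gives 1.77-1.92.

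**Set against sampling error**

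The 95% error factor of one GMR is 10^(t × SD × √(1/n1 + 1/n2)), with an assumed log10 SD of 0.4-0.6 and 15% carriers:

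- 30 vs 170 children: 1.43 to 1.72
- 15 vs 85 children: 1.67 to 2.16

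The largest shift above is 2/1.77 = 1.13-fold. For the proportions, the shift at u = 10% is 1 point (p = 10%) or 3 points (p = 30%). The approximate 95% half-width 1.96√(p(1 − p)/n) is 4.2-5.9 points at 10% and 6.4-9.0 points at 30%, for n = 200 and n = 100.

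**Effect of the missing-value reading**

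Dropping 2-10% of children from the regression widens the log-scale interval by about 1/√0.98 = 1.01 to 1/√0.90 = 1.05, if the loss is even across groups and unrelated to antibody. The unadjusted cohort GMR does not use carriage and is the same under both readings.

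**The case for a change.** The best case for a change is that the complete-case rule in SAP 5.3 has nothing to act on if the definition already calls the child a non-carrier. A programmer must therefore choose, and no planned count would reveal the choice for children without a usable culture. The repair looks cheap: one definition and one count. The exposure is clearest at an interim summary, because SAP 7 makes that depend only on assay data, and types could still be pending.

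The interim case can be sized. Assume 200 unvaccinated children, 30% with pneumococcus (60 isolates), and a VT share of 75-92%, borrowing the regional coverage range in Protocol 1, which is not stated to be carriage data. With 30 isolates untyped and their children coded as non-carriers, VT carriage reads 22.5/200 = 11.3% to 27.6/200 = 13.8%, against a true 45/200 = 22.5% to 55.2/200 = 27.6%. A GMR of 2 reads 1.83 to 1.79.

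Excluding the untyped children hardly mends the proportion. They all come from the pneumococcus-positive side, so carriage would still read 22.5/170 = 13.2% to 27.6/170 = 16.2%. What helps is waiting for the types, which the final report already does. Interim summaries are optional and carry no decision rule.

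It stands that the text names no unknown status and that children without a usable culture go uncounted in the planned tables. It also stands that the two readings differ in N. The repair is less simple than it looks, since the documents give no criteria for a valid culture on which to base the definition.

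**Conclusion.** No change to the plan follows. This is a missing detail of a familiar kind: carriage is derived from the culture result and the imported serotype, and an analyst who finds neither will ordinarily leave it missing, let SAP 5.3 apply to the regression, and show the N. Followed as written, the plan aspirates every child, types every isolate and reports after all data are in, so few children should be affected.

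Under the assumed 2-10% without a usable culture, the literal reading moves a GMR of 2 to 1.94-2.00, or to between 1.77 and 2.14 if those children also differ two-fold in antibody at 5-10% unknown. Every one of these shifts is smaller than the sampling error of a single subgroup GMR. The study is descriptive, with no hypotheses and no decision rule.

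The conclusion rests on the unknown share staying near this range, which the documents support by design but do not quantify. Should many children turn out to lack a culture, the four-subgroup results would need to be read with that in mind.

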6.1.2. Sensitivity/Supplementary Analyses

Not applicable.

6.2. Baseline and Other Summaries and Analyses

6.2.1. Baseline Summaries

Subjects demographics (collected information including, sex, residence, and number of siblings, if any) and medical history will be descriptively summarized.

6.2.2. Deep Upper Respiratory Aspirates Culture Summaries

The number and proportion of subjects with *S. pneumoniae* isolates detected will be summarized for both cohorts: the 13vPnC cohort and unvaccinated cohort. Additionally, the number and proportion of each serotype, serotype included in 13vPnC (VT), and serotypes not included in 13vPnC (non-VT) will be summarized for both cohorts.

6.2.3. Adverse Events

Any AEs reported in the study will be listed.

7. INTERIM ANALYSES

Interim data may be summarized if the assay data is available for subjects enrolled by certain cutoff date. Final report will be summarized after all data are available.

